3.5.2. Laboratory Data

Laboratory testing will be performed at screening and may be performed at unplanned safety assessment or early termination visit. The tests detailed in the table below will be performed by the central laboratory.

Laboratory Assessments	Parameters			
Hematology	Platelet Count	White blood cell (WBC) count with Differential: Neutrophils Lymphocytes Monocytes Eosinophils Basophils		
	Red blood cell (RBC) Count			
	Hemoglobin			
	Hematocrit			
Clinical Chemistry ¹	Albumin	Bicarbonate or total carbon dioxide (CO ₂)	Creatinine	Total Protein
	Alanine Aminotransferase (ALT)	Blood urea nitrogen (BUN)	Glucose (nonfasting)	Sodium
	Alkaline phosphatase	Calcium	Potassium	Hemoglobin A1c
	Aspartate Aminotransferase (AST)	Chloride	Total bilirubin	
Other	Prothrombin time (PT)/ international normalized ratio (INR), follicle stimulating hormone (FSH) ²			

NOTES:

¹ Details of liver chemistry stopping criteria and required actions and follow-up assessments after liver stopping or monitoring event are given in Appendix 5. All events of ALT $\geq 3 \times$ upper limit of normal (ULN) and bilirubin $\geq 2 \times$ ULN ($>35\%$ direct bilirubin) or ALT $\geq 3 \times$ ULN and INR >1.5 , if INR measured which may indicate severe liver injury (possible Hy's Law), must be reported as an SAE (excluding studies of hepatic impairment or cirrhosis).

² For confirmation of postmenopausal status only.

3.5.3. Vital Signs

Vital signs will be assessed at screening and unplanned safety assessment or early termination visit.

3.5.4. Physical Examinations, Including Height and Weight

A complete physical examination will be assessed at screening and may be performed at unplanned safety assessment or early termination visit.

3.5.5. Electrocardiograms

A single lead ECG will be performed at screening and may be performed at unplanned safety assessment or early termination visit.

4. ANALYSIS SETS (POPULATIONS FOR ANALYSIS)

For purposes of analysis, the following analysis sets are defined:

Population	Description
Screened	All participants who sign the informed consent form (ICF).
Enrolled	All participants who sign the ICF and are not screen failure.
Randomly Assigned to Study Intervention	All participants who are randomized.
Full Analysis Set (FAS)	All participants who are randomly assigned to study intervention and apply at least 1 dose of study intervention. Participants will be analyzed according to the intervention they are randomized. For change from baseline or percent change from baseline endpoints it would require that a participant have a baseline value and at least one post-baseline value to be included in the analysis for that endpoint. For the endpoint with a threshold requirement for change from baseline, only participants with a baseline value \geq the threshold will be included in the analysis.
Safety Analysis Set (SAF)	All participants who are randomly assigned to study intervention and apply at least 1 dose of study intervention. Participants will be analyzed according to the intervention they actually received.
Full Analysis Set-Interim Analysis (FAS-IA)	All participants who are randomly assigned to study intervention and apply at least 1 dose of study intervention and complete 6 weeks treatment or early discontinue study intervention at the IA cutoff date. Participants will be analyzed according to the intervention they are randomized.
Safety Analysis Set-Interim Analysis (SAF-IA)	All participants who are randomly assigned to study intervention and apply at least 1 dose of study intervention and complete 6 weeks treatment or early discontinue study intervention at the IA cutoff date. Participants will be analyzed according to the intervention they actually received.

5. GENERAL METHODOLOGY AND CONVENTIONS

Final analyses will occur after database lock after Last Participant Last Visit (LPLV).

5.1. Hypotheses and Decision Rules

This protocol is designed to establish the superiority of crisaborole 2% BID to vehicle for the primary endpoint percent change from baseline in the TSS at Week 6/EOT (based on in person assessment by HVP at the home visit). The null hypothesis is that there is no difference between crisaborole arm and vehicle arm, and the alternative hypothesis is that there is a significant difference between crisaborole arm and vehicle arm. Specifically, the alternative hypothesis is that the mean percentage improvement from baseline for crisaborole group is 22% greater than vehicle group. The significance level is 5% one-sided. The interim analysis (if conducted) is an administrative interim analysis; no adjustment of p-values is planned for the analysis of the final study data.

5.2. General Methods

In general, number, percent and 90% confidence interval (CI) will be presented for binary endpoints. Descriptive summary statistics (n, Mean, Standard deviation (Std), Median, Min., Max.) will be presented for continuous endpoints. In addition, graphics may be used to present the data.

Day 1 will be the date when a participant applies the first dose of study intervention. Baseline value will be the last non-missing assessment on or before Day 1 and prior to first dose of study intervention. **CCI**

5.2.1. Analyses for Continuous Data

Analysis of Variance (ANOVA)/Analysis of Covariance (ANCOVA) for Non-longitudinal Continuous Data:

The non-longitudinal continuous data will be analyzed by ANOVA with treatment as the factor. ANCOVA will be used if relevant baseline value and/or other factors are included as covariates. Comparison of crisaborole ointment, 2%, BID to vehicle (providing LSM of the treatments, LSM of the treatment difference, 1-sided p-value and 90% CI) will be generated.

Mixed Effect Model Repeat Measurement (MMRM) for Longitudinal Continuous Data:

The longitudinal continuous endpoints will be analyzed with MMRM that includes fixed effects of treatment group, visit, and treatment-group by visit interaction, without imputation for missing values. If the endpoint is change from baseline, baseline will be included in the model as a covariate. A common unstructured variance-covariance matrix will be used, provided it converges. If this is a convergence issue, other type of covariance matrix such as first order autoregressive (AR[1]), compound symmetry will be used. Comparison of crisaborole ointment, 2%, BID to vehicle (providing least squares means [LSM] of the treatments, LSM of the treatment difference, 1-sided p-value and 90% CI) at each time point during the first 6 weeks will be generated using this model.

5.2.2. Analyses for Binary Data

For binary endpoint at each time point, large sample approximation to the difference in binomial proportions will be used for testing (Normal Z-test) the superiority of crisaborole ointment, 2%, BID to vehicle and for forming 90% CI's and calculating 1-sided p-values.

For non-longitudinal binary endpoints, data at Week 6 or EOT will be included in the analysis.

For analysis of longitudinal binary endpoints, observations after the discontinuation of study intervention or missing values for any reason will be handled by setting the endpoint to nonresponsive. Note that this is a composite endpoint in the sense that a response requires the participant completes a visit of interest eg, Week 6, and achieves a response per the

defined response criteria (otherwise it is considered a nonresponse). This method of handling missing response is known as missing response as non-response (MR-NR). For a single time point (eg, ISGA Clear (0) or Almost Clear (1) with at least a 2-grade improvement from baseline at Week 6), large sample approximation to the difference in binomial proportions will be used for testing (Normal Z-test) the superiority of crisaborole ointment, 2%, BID to vehicle and for forming 90% CI's and calculating p-values. The analysis will be based on Estimand 2 using FAS.

5.2.3. Analyses for Categorical Data

The frequency and percentage for each category will be presented for category endpoints.

5.3. Methods to Manage Missing Data

5.3.1. Binary Endpoints

For non-longitudinal binary endpoints, there is no imputation for missing data, data at Week 6 or EOT will be included in the analysis.

For longitudinal binary endpoints analyzed at each scheduled visit separately, participants with missing data at a time point for any reason will be defined as MR-NR at that time point in the intervention period.

5.3.2. Continuous Endpoints

For non-longitudinal continuous data, primary analysis will be based on the observed cases, there is no imputation for missing data.

For continuous efficacy endpoints measured longitudinally, missing values post-baseline will be handled in a MMRM. For longitudinal continuous endpoints, assuming that the missing data mechanism is missing at random (MAR), the data will be analyzed using a MMRM model for these continuous variables (see [Section 5.2.1](#)). Under an assumption that the missing data mechanism is MAR, this model will yield unbiased estimates and valid inferences for treatment effects assuming all participants maintain therapy.

6. ANALYSES AND SUMMARIES

6.1. Primary Endpoint

6.1.1. Primary Analysis

The primary endpoint is percent change from baseline in the TSS at Week 6/EOT based on HVP in-person assessment.

- Estimand strategy: while-on-treatment, Estimand 1 ([Section 2.1.2](#))
- Analysis set: FAS ([Section 4](#))
- Variable: Percent change from baseline to Week 6/EOT in TSS
- Analysis method: ANOVA in [Section 5.2.1](#)

- Intercurrent event: All data after an intercurrent event (eg, discontinuation of treatment), if collected, will be excluded; data at Week 6 or EOT (within date of last dose + 10 days) will be included.
- The LSM along with the corresponding standard error (SE) for each treatment group, LSM difference along with the corresponding SE, 90% CI, and p-value will be presented. $LSM \pm SE$ will also be presented graphically by treatment group.

6.1.2. Sensitivity Analyses

Two sensitivity analyses will be performed for the percent change from baseline in the TSS at Week 6 based on HVP in-person assessment.

1. Observed cases: Principal Stratum estimand will be used. The data after an intercurrent event discontinuation of study intervention, if collected, will be excluded, only no-missing observed cases in-person assessment at Week 6 (based on window definition in Table 3) will be included in the analysis. No imputation for missing data. ANOVA ([Section 5.2.1](#)) will be used. The LSM along with the corresponding SE for each treatment group, LSM difference along with the corresponding SE, 90% CI, and 1-sided p-value will be presented. The data after an intercurrent event, if collected, will be excluded, observed cases at Week 6 will be included.

2. Multiple imputations: Hypothetical estimand will be used. The data after an intercurrent event discontinuation of study intervention, if collected, will be excluded, observed cases in-person assessment at Week 6 (based on window definition in Table 3) will be included in the analysis. Missing TSS at Week 6 will be imputed using the method of MCMC multiple imputation under MAR assumption. Multiple imputation and subsequent analysis will involve the following four principal tasks:

- 1) Calculate the total number of missing values to be imputed by MCMC (nmiss) for Week 6 value.
- 2) Create a data set, one for each treatment group, of participants with observed values and those needing imputation by MCMC. The missing TSS values in each data set will be filled in using the MCMC method “ $10 \times nmiss$ ” times to generate “ $10 \times nmiss$ ” data sets. The resulting data sets for each treatment group will be combined into one complete data set by imputation. The imputed values will be rounded to the nearest integer of 0 - 12.
- 3) For each complete data set, derive % change from baseline in TSS at Week 6. The estimated treatment effect and its standard error for each complete data set will be calculated using ANOVA ([Section 5.2.1](#)).
- 4) Combine the estimated treatment effects and standard errors from the above into a single inference using Rubin’s formulae as implemented in SAS PROC MIANALYZE.

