Estimand 3: The third estimand of this study is a hypothetical estimand, which estimates the treatment effect of crisaborole compared with vehicle at each time point under the scenario of no discontinuation of study intervention. It includes the following 5 attributes:

- Population: participants ≥ 45 years of age with SD without active skin ulceration;
- Variable: percent change from baseline in TSS at each time point;
- Treatment condition: crisaborole 2% BID or vehicle;
- Intercurrent event: all data collected after any intercurrent events will be excluded;
- Population-level summary: difference in mean percent change from baseline in TSS at each time point between crisaborole ointment, 2%, BID and vehicle.

Estimand 3 will be used in analyzing the longitudinal continuous endpoints.

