9. APPENDICES

Appendix 1. Summary of Efficacy Analyses

Endpoint	Analysis Type	Population	Data Inclusion and Rules for Handling Intercurrent Events and Missing Data	Analysis Model
Percent Change from baseline to Week 6/EOT in TSS based on HVP in-person assessment	Summary	FAS	observed data	N/A
	Main analysis	FAS	The data after an intercurrent event, if collected, will be excluded, data at Week 6 or EOT (within date of last dose +10 days) will be included.	ANOVA with term treatment
	Sensitivity analysis	FAS	The data after an intercurrent event, if collected, will be excluded, observed cases at	ANOVA with term treatment

			Week 6 will be included. No imputation for missing data.	
	Sensitivity analysis	FAS	The data after an intercurrent event, if collected, will be excluded, observed cases at Week 6 will be included. Missing data at Week 6 will be derived for the analysis using the method of multiple imputation.	ANOVA with term treatment
Percent Change from baseline to Weeks 1 - 6 in TSS based on central readers assessment	Summary	FAS	observed data	N/A
	Main analysis	FAS	The data after an intercurrent event, if collected, will be excluded. Missing data will not be imputed.	MMRM with terms treatment, visit, and interaction of treatment and visit
ISGA success and ISGA clear/almost clear at Week 6/EOT based on HVP in-person assessment	Main analysis	FAS	The data after an intercurrent event, if collected, will be excluded, data at Week 6 or EOT will be included.	Normal approximation
ISGA success and ISGA clear/almost clear at Weeks	Main analysis	FAS	A participant with a missing observation or after an	Normal approximation

1- 6 based on central readers assessment			intercurrent event of discontinuation of treatment will be considered a non-responder for the visit of interest	
Percent change from baseline in %BSA at Week 6/EOT based on HVP in-person assessment	Summary	FAS	observed data	N/A
	Main analysis	FAS	The data after an intercurrent event, if collected, will be excluded, data at Week 6 or EOT will be included.	ANOVA with term treatment
Percent change from baseline in %BSA at Weeks 1-6 based on central readers assessment	Summary	FAS	observed data	N/A
	Main analysis	FAS	The data after an intercurrent event, if collected, will be excluded. Missing data will not be imputed.	MMRM with terms treatment, visit, and interaction of treatment and visit

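### Primary endpoint: sensitivity analysis 1 is called a principal stratum estimand but is an observed-case ANOVA; no analysis tests missingness related to the unseen outcome, and the imputation may miss leavers with no in-person score

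*SAP*

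**What the plan says.** Four parts of the SAP bear on this.

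- **Item 1 of SAP 6.1.2:** "Observed cases: Principal Stratum estimand will be used". The method is the Section 5.2.1 ANOVA on in-person TSS observed in the Table 3 Week 6 window, without imputation. SAP 2.1.2 defines three estimands: while-on-treatment, composite and hypothetical ("Estimand 3: The third estimand of this study is a hypothetical estimand"). A principal stratum is not among them.
- **Item 2 of SAP 6.1.2:** "Missing TSS at Week 6 will be imputed using the method of MCMC multiple imputation under MAR assumption". The first step is "Calculate the total number of missing values to be imputed by MCMC (nmiss) for Week 6 value"; each arm is then imputed separately, and the number of data sets is ten times that count. Appendix 1 runs this on the FAS: "Missing data at Week 6 will be derived for the analysis using the method of multiple imputation".
- **Primary analysis, SAP 5.3.2:** "For non-longitudinal continuous data, primary analysis will be based on the observed cases, there is no imputation for missing data". SAP 6.1.1 includes early-termination scores taken up to 10 days after the last dose.
- **FAS, SAP Section 4:** for percent-change endpoints a participant must "have a baseline value and at least one post-baseline value to be included in the analysis for that endpoint". The FAS in protocol 9.3 has no such condition. The SAP version history says these in-person endpoints have a single post-baseline assessment.

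A conservative missing-data rule does exist elsewhere. For longitudinal binary endpoints, "participants with missing data at a time point for any reason will be defined as MR-NR". That covers Central Reader ISGA, which is a different endpoint and a different rater.

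**The concern.** Participants with a Week 6 score on crisaborole and those with one on vehicle are two groups selected after randomization. They represent the same principal stratum (people who would stay on either treatment) only under an assumption such as dropout unrelated to treatment and outcome, and the SAP states none. The label therefore invites a causal reading that the ANOVA does not support.

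The three inferential analyses of the primary endpoint also share a blind spot. Two use observed cases. The third imputes leavers as though they resembled stayers in the same arm. If crisaborole participants leave because they respond badly, all three move together, and their agreement says nothing about robustness.

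Finally, if the Section 4 rule governs item 2, a leaver with no in-person post-baseline score is never imputed. Item 2 would then mainly impute people whose early-termination score before Day 40 is known and already in the primary analysis. A tipping-point analysis built on that base would look more reassuring the fewer leavers had been scored.

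**Working it through.** **Inputs.** Protocol 9.2: 35 per arm, difference 22, SD 35, one-sided 5%. Assumed, because the current sample size section gives no dropout rate: the number without a Week 6 score and how strongly leaving depends on response. Percent change is expressed as improvement.

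**Plan's own figure.** SE = 35·√(2/35) = 8.37; power = Φ(22/8.37 − 1.645) = 83.8% (83.1% with the t distribution). The stated power of at least 80% reproduces.

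**Analyses of the primary endpoint, side by side.** Primary: observed Week 6/EOT values. Item 1: observed Week 6 values. Item 2: MI under MAR within arm. Appendix 1 adds only a descriptive summary, and protocol 9.4.2 defers the detail to the SAP.

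**Reach of item 2 and tipping points.** Suppose 35 are dosed per arm and 4 per arm have no Week 6 score, so 31 are observed. Shift only the imputed crisaborole values, by δ. Let N be the number analysed per arm, m the number imputed, f = m/N, and k = 30/28 = 1.071 (the variance inflation in proper normal imputation from 31 values). With many imputations:

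- Within-imputation variance: W = (2/N)·35²·[1 + f(k − 1)]
- Between-imputation variance: B = 2·f²·k·35²·(1/31 + 1/m)
- Variance added by the shift: A(δ) = f(1 − f)·δ²/(N − 1)
- The result D tips where D − f·δ = 1.645·√(W + B + A(δ))

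| Reading of item 2 | N | m | Data sets | SE | One-sided p at 22 / 16 | Tipping δ at 22 / 16 |
|---|---|---|---|---|---|---|
| (a) all dosed imputed | 35 | 4 | 80 | 8.96 | 0.0070 / 0.0371 | 56.2 / 10.8 |
| (b) FAS rule, 2 of 4 have an early score | 33 | 2 | 40 | 8.93 | 0.0068 / 0.0365 | 96.7 / 20.6 |
| (c) FAS rule, none of 4 has a score | 31 | 0 | 10 × 0 = 0 | 8.89 | 0.0081 / 0.0385 | none exists |

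- (a): f = 0.1143, W = 70.57, B = 9.68, SE = √80.25 = 8.96. At δ = 56.2 the estimate is 22 − 6.42 = 15.58, A = 9.40, and 1.645·√89.65 = 15.58.
- (b): f = 0.0606, W = 74.56, B = 5.13, SE = √79.69 = 8.93. At δ = 96.7 the estimate is 22 − 5.86 = 16.14, A = 16.64, and 1.645·√96.33 = 16.15.
- (c): SE = 35·√(2/31) = 8.89, 60 df. Item 2 equals item 1.

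Small-sample degrees of freedom change (a) to 54.7 and 9.1. From (a) to (b) the apparent robustness nearly doubles although two people per arm are wholly unknown.

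**On the planned integer 0–12 scale.** This was simulated with an assumed baseline mean of 5 to 7 and SD of 2. The median tipping shift in (a) is 2.5 to 4.0 TSS points at a difference of 22, and 0.5 to 0.75 at 16.

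**Shift that none of the three analyses would show.** Let only crisaborole's dropout depend on outcome, with no score for its leavers. With Z the standardized improvement and q(z) = 1/(1 + exp(−(a − ln(OR)·z))), where a is set so that q averages to p, the stayer mean moves by 35·E[Z(1 − q(Z))]/(1 − p):

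| Dropout p | OR 1.5 per SD | OR 2 | OR 3 |
|---|---|---|---|
| 5% | 0.70 | 1.18 | 1.79 |
| 10% | 1.40 | 2.32 | 3.42 |
| 15% | 2.08 | 3.42 | 4.98 |

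Losing exactly the worst 10% gives 35·φ(1.2816)/0.9 = 6.82. At 10% and OR 2, a true 22 reads as 24.3. The leaver–stayer gap is 2.32/0.10 = 23.2, so δ = 23.2 with all dosed participants imputed restores 24.3 − 0.10 × 23.2 = 22.0. Under (c) no δ can.

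**Label.** In the same case the gap between item 1 and the stratum effect is r × 2.32, where r is the correlation of a person's outcomes under the two treatments: 0.70 at r = 0.3 and 1.85 at r = 0.8. A harsher simulation (20% versus 5% loss, log-odds 1.5 per SD) gave an observed-case difference of 27.6 against a stratum effect of 22.8 to 25.5. With 10% loss in each arm the two agreed at 22.0.

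**The case against.** The strongest reply concerns weight.

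- **The FAS point is inference.** SAP 6.1.2 is the specific instruction and says missing Week 6 TSS is imputed; Section 4 is a general rule and does not say whether the post-baseline value must be an in-person one. A reading that orders zero data sets is the less natural one. On the p-values above, the choice of reading moves the result by only 0.001 to 0.002. This stands as a reason to call the reach unclear; it does not remove the ambiguity for the programmer.
- **The tipping-point contrast describes an analysis not yet planned.** True. Its use is to show that the imputation population must be settled before such an analysis is added.
- **Effects are small and assumed.** The central shift of 2.3 points is about a quarter of the SE (2.3/8.9 = 0.26), and it vanishes under balanced loss. This stands.
- **The plan already limits the gap.** Early leavers with a score stay in the primary analysis. Participants who only stop treatment are asked to attend the EOT visit, and protocol 7.2 expects withdrawal to be uncommon. Central Reader TSS uses weekly images from leavers as well. However, that MMRM also assumes MAR and uses another rater, and at study withdrawal the visit is held only where feasible.
- **This is a Phase 2a proof-of-concept study.** That argues for a modest addition. It does not justify a wrong estimand label.

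**Conclusion.** The concern holds. The label on item 1 is wrong as written, and every inferential analysis of in-person TSS is either observed-case or MAR; both follow directly from the text. That item 2 omits leavers with no in-person score is the literal reading of Section 4 together with Appendix 1, and it is an inference.

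The primary test and the interim criterion are unaffected. The loss is in what the sensitivity analyses can support, mainly if the result is borderline or dropout is unequal. Under the stated assumptions the shift that would go unseen is 0.7 to 5.0 points, with 2.3 as the central case. Its sign reverses if vehicle is the arm that loses poor responders. With 4 of 35 missing per arm, a result at the design effect of 22 is robust and a result of 16 is not. All of these sizes rest on assumed dropout.

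**What to change.** 1. In SAP 6.1.2 item 1, delete the principal stratum label and call it a supplementary observed-case analysis.
2. State that item 2 imputes Week 6 TSS for all randomized and dosed participants with a baseline value, including those with no post-baseline score, and reconcile this with the FAS rule in Section 4.
3. Then add a delta-adjusted (tipping-point) version of that imputation. Shift imputed Week 6 TSS separately by arm, including worsening crisaborole only, and report where the one-sided p-value crosses 0.05.
4. Minor: add one clause on scores taken on or after Day 40 when dosing stopped before Day 40. The Table 3 window admits them up to 10 days after the last dose, but 6.1.2 also excludes data after discontinuation and, unlike 6.1.1, does not say which governs.

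The cost is SAP wording and a short extension of an imputation program already planned. The claim made for item 1 becomes weaker.
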